LSRs will be summarized by treatment group by the most intense score for each LSR and by the sum score at each visit and over the course of the study. The frequency of the individual LSRs will be tabulated by severity and treatment group at each visit.

Sponsor Name: Actavis, LLC Protocol: 094-3153-301, v1.0

SCHEDULE OF EVENTS

Visit	Visit 1	Visit 2 Telephone	Visit 3	Visit 4	Visit 5 Telephone	Visit 6	Visit 7
Week	Screening/ Baseline	Week 1	Week 2	Week 4	Week 5	Week 6	Week 14/ EOS
Day	Day 1	Day 8 (± 2 days)	Day 15 (+ 3 days)	Day 29 (± 2 days)	Day 36 (± 2 days)	14-17 Days After Visit 4	Day 99 (± 4 days)
Treatment Period	Treatme Trea	nt Cycle = To tment Cycle	est Article A 1-Visit 1 to	pplication O Visit 3 Treat	nce Daily for ment Cycle 2	· 14 Consecut 2-Visit 4 to V	tive Days isit 6
Informed Consent ¹	X						
Medical History, Demographics	X						
Concomitant Medications	X		X	X		X	X
Brief Physical Exam including Dermatologic Exam and Vital Sign Assessment	X						
Inclusion/Exclusion Criteria	X						
Treatment Area (Face or Balding Scalp) ID - Location & Size	X						
AK Lesion Count	X					X	X
Local Skin Reaction Assessment	X		X	X		X	X
Confirm Next Visit Appointment, Review Dosing Instructions and Query About AEs.		X			X		
Pregnancy Testing ² for WOCBP ³	X						X
Issue Subject Diary	X			X			
Collect & Review Subject Diary for Compliance			X			X	
Adverse Events	X	X	X	X	X	X	X
Dispense/Return/Weigh Test Article (Perform Drug Accountability)	X		X	X		X	

¹ Informed consent may be obtained within 30 days prior to the Baseline Visit.

² Urine pregnancy tests must have a minimum sensitivity of 25 mIU β-hCG/mL of urine and must be performed within 24 hours prior to the start of test article at baseline.

³ See Section 14.4 for definition of woman of childbearing potential (WOCBP).

Sponsor Name: Actavis, LLC Protocol: 094-3153-301, v1.0

ABBREVIATIONS

5-FU 5-Fluorouracil

ADR Adverse Drug Reaction

AE Adverse Event

AHA Alpha Hydroxy Acid

AK Actinic Keratosis or Keratoses

BSA Body Surface Area

CLIA Clinical Laboratory Improvement Amendments

CFR Code of Federal Regulations

CRF Case Report Form EOS End of Study

EDC Electronic Data Capture

FDA Food and Drug Administration

GCP Good Clinical Practices

HIV Human Immunodeficiency Virus

ICF Informed Consent Form

ICH International Conference on Harmonization

IEC Independent Ethics Committee

IFN Interferon IL Interleukin

IRB Institutional Review Board

ITT Intent-to-Treat
IUD Intrauterine Device

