6.2 Instructions for Use and Application

Subjects will be instructed to apply test article once daily approximately 1 to 2 hours before bedtime to the skin of the treatment area (either full face (excluding the ears) or balding scalp) for two, 2-week treatment cycles separated by a 2-week no-treatment period. Subjects will apply test article for 14 consecutive days for each treatment cycle, regardless of the visit window. However, if a subject did not apply for 14 consecutive days due to a dose held or missed, and 14 consecutive days has elapsed from baseline, then no additional test article will be applied to make up for missed or held doses. Test article should be applied as a thin film to the entire treatment area and rubbed until the cream is no longer visible. Up to two (2) full actuations of the pump may be dispensed and applied to the treatment area at each application. Subjects will be cautioned to avoid applying the cream to the lips, nostrils and periocular areas. The test article should be left on the skin for approximately eight (8) hours, after which time the test article should be removed by washing the area with mild soap and water. Treatment should continue for

Sponsor Name: Actavis, LLC Protocol: 094-3153-301, v1.0

the full treatment course even if all AKs appear to be gone. The study staff should demonstrate the proper use of the pump and application technique using the pumps containing the vehicle cream provided for subject training. See **Appendix 1** for the complete Subject Instructions.

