9.1 Visit 1 (Screening/Baseline, -30 to Day 1)

Informed consent may be collected from study subjects up to 30 days before Visit 1. If applicable, qualified subjects can washout from prohibited medications or treatments prior to their Screening/Baseline Visit once informed consent has been obtained. If washout period exceeds 30 days, re-consent is required. The Screening and Baseline Visit may be completed on the same day, if no washout is required.

At this visit, the investigator or designee will:

- Obtain a signed, written informed consent and update the Subject Screening and Enrollment Log.
- Confirm the subject meets the inclusion/exclusion criteria.
- Document the information required on the Medical History form.
- Document the information required on the Demographics form.
- Record the subject's prior and/or concomitant therapies.

Sponsor Name: Actavis, LLC Protocol: 094-3153-301, v1.0

If the subject requires washout from previous medications, the remaining activities will be performed after washout is complete.

- Perform a limited physical exam including a brief dermatologic exam and vital sign assessment. Consistent with Exclusion Criterion #13, any subject with a suspicious lesion within the treatment area should not be enrolled prior to confirmation that the lesion is not skin cancer. In the event that a biopsy is warranted to make such a determination per the investigator, such a procedure is considered outside the scope of this study and therefore will be the responsibility of the potential subject. In the event that a biopsy is needed and it is not available for review, the subject shall be considered a screen failure.
- Identify the treatment area; either the full face or balding scalp.
- Estimate %BSA of the treatment area.
- Perform the AK lesion count (≥ 4 mm in diameter as well as any smaller lesions) and estimate the surface area of the entire treatment area (full face or balding scalp) to be treated as described in **Section 10.1**. (Note: A minimum of 5 to a maximum of 20 AKs ≥ 4 mm in diameter in the treatment area is required to qualify).
- Document the diameter of each AK lesion in the treatment area.
- Perform the LSR assessment as described in **Section 10.2**.
- Reaffirm the Inclusion/Exclusion criteria.
- Perform a UPT for all WOCBP. The UPT must be negative for subjects to continue.

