- Assign the subject the next available (lowest) subject number in ascending order. Assign the subject the lowest available test article kit number and dispense two test article pumps from the kit. NOTE: The pumps will be weighed prior to being dispensed.
- Review and dispense a Subject Instruction Sheet to the subject (see **Appendix 1**). Instruct the subjects to apply test article for 14 consecutive days and demonstrate proper use of the pump and test article application using vehicle cream pumps provided for subject training.
- Issue the subject diary.
- Confirm the next visit.

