17.3.1 Efficacy Analyses

The primary efficacy endpoint is the complete clearance rate (treatment success), defined as the proportion of subjects at the EOS visit in the PP population with a count of zero AK lesions in the treatment area. All AKs (baseline and new lesions) independent of size within the treatment area will be included in the efficacy lesion count for each visit.

The 90% Wald's confidence interval with Yate's continuity correction will be constructed on the difference between the proportions of subjects with lesion clearance in the Test and Reference treatments to evaluate the therapeutic comparability of the two active treatments. Two-sided, continuity-corrected Z-tests will be used to evaluate the superiority of each active treatment's clearance proportion over that of the Vehicle treatment.

If the 90% confidence interval on the difference between the Test and Reference lesion clearance proportions is contained within the interval -0.20 to +0.20, and each of these proportions is greater than, and statistically different (p<0.05) from, the Vehicle proportion, then the Test and Reference products will be considered to be therapeutically equivalent.

The therapeutic comparability evaluations in the PP population will be considered primary while those in the ITT will be considered supportive. The superiority comparisons in the ITT population will be considered primary while those in the PP population will be considered supportive.

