6 EFFICACY AND SAFETY MEASUREMENTS

6.1 Efficacy Measurements

6.1.1 AK Lesion Counts

AK lesion counts within the Treatment Area (full face or balding scalp) will be performed at Visits 1, 6 and 7 by the investigator or qualified designee. All AK lesions (baseline AKs and new AKs), independent of size, in the Treatment Area will be identified, counted, and recorded. The number of AK lesions in the Treatment Area that are 4 mm in diameter and the diameter of each AK lesion in the treatment area will be documented at the Baseline Visit. The Treatment Area at Baseline must include 5 to 20 clinically typical, visible or palpable AKs each at least 4 mm in diameter, in an area greater than 25 cm²on either the face (excluding ears) or the balding scalp, but not both. At Visits 6 and 7, the number of total AK lesions in the treatment area will be counted and the number of new AKs will be identified. A new AK is defined as a lesion that was not present at the Baseline Visit.

If the AK count cannot be performed due to a LSR this will be documented on the CRF.

The AK clearance rate for a subject will be calculated as follows: {1 - [(#AKs at follow-up)/ (#AKs at Baseline)]}* 100.

Therefore, if the AK count at follow-up is 0, the clearance rate will be 100%, i.e., complete clearance of AK lesions.

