8.7 Efficacy Analyses

8.7.1 Primary Efficacy Analyses

The primary efficacy endpoint is the complete clearance rate (treatment success), defined as the proportion of subjects in the **PP** population at the EOS visit with 100% clearance of AK lesions in the Treatment Area. All AKs (baseline and new lesions) independent of size within the treatment area will be included in the efficacy lesion count for each visit.

The 90% Wald's confidence interval with Yate's continuity correction will be constructed on the difference (generic imiquimod minus Zyclara) in the proportions of subjects with complete lesion clearance to evaluate the therapeutic comparability of the two active treatments.

Two-sided, continuity-corrected Z-tests will be used to evaluate the superiority of each active treatment's complete clearance rate over that of the Vehicle treatment.

If the 90% confidence interval on the difference between the Test and Reference lesion complete clearance rates at EOS in the **PP** population is contained within the interval -0.20 to +0.20, and each of these proportions in the ITT population is greater than, and statistically different (p<0.05) from, the Vehicle proportion in the ITT population at EOS, then the Test and Reference products will be considered to be therapeutically equivalent.

The therapeutic comparability evaluations in the PP population will be considered primary while those in the ITT will be considered supportive. The superiority comparisons in the ITT population will be considered primary while those in the PP population will be considered supportive.

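### Does the equivalence conclusion need an analysis adjusted for baseline lesion count and for face or scalp location?

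*SAP*

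**What the plan says.** SAP 8.7.1 sets the equivalence comparison: "The 90% Wald's confidence interval with Yate's continuity correction will be constructed on the difference (generic imiquimod minus Zyclara) in the proportions". It must lie within -0.20 to +0.20 in the per-protocol (PP) population. For vehicle, the same section says: "Two-sided, continuity-corrected Z-tests will be used to evaluate the superiority of each active treatment's complete clearance rate over that of the Vehicle treatment", with the intent-to-treat (ITT) population primary. Protocol 17.3.1 uses the same interval: "The 90% Wald's confidence interval with Yate's continuity correction will be constructed on the difference between the proportions of subjects with lesion clearance". No readable text in either document adds a covariate or stratum.

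The two candidate covariates are collected. Protocol 9.1 instructs the site: "Perform the AK lesion count (≥ 4 mm in diameter as well as any smaller lesions". Later in the same visit list comes: "Assign the subject the lowest available test article kit number and dispense two test article pumps from the kit". SAP 6.1.1 confirms that the count covers every size: "All AK lesions (baseline AKs and new AKs), independent of size, in the Treatment Area will be identified, counted, and recorded". The Schedule of Events has a Visit 1 row reading "Treatment Area (Face or Balding Scalp) ID - Location & Size".

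SAP 8.6.1 summarises total baseline lesion count and the count of lesions of at least 4 mm. Protocol 17.3 has baseline characteristics tabulated by arm in both ITT and PP. Equivalence in ITT is a planned supportive analysis. SAP section 2 allows unplanned analyses if the study report identifies them as such.

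**The concern.** Clearance means zero lesions, so a subject who starts with 20 plausibly has a harder task than one who starts with 5. If count predicts clearance, it is a natural adjustment variable, and here it costs nothing to obtain. Location is a weaker candidate. Protocol 6.2 sets one ceiling for face and scalp ("Up to two (2) full actuations of the pump may be dispensed and applied to the treatment area at each application"), so the amount per unit area might differ, but a ceiling applied as a thin film does not establish that it does.

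The sharper part of the worry is the analysis set. PP membership depends on compliance, the visit window, protocol violations and the reason for discontinuation, all of which arise after randomisation. Random assignment does not guarantee balance in such a subset. If one active arm lost more high-count subjects than the other, the unadjusted PP difference would shift. The ITT analysis changes the population but does not isolate that shift. What would be at stake is a conclusion of equivalence, or of its absence, that reflects who was left in the PP set.

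**Working it through.** **Inputs.** From the documents: 435 ITT subjects, margin ±0.20, a 90% Wald interval with continuity correction, and 5 to 20 qualifying lesions at baseline. The clearance rates, allocation ratio, PP loss and any effect of count or location on clearance are not readable or not given. The sample size of 435 therefore cannot be reproduced, and the following are assumptions:

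- 30% clearance in each active arm.
- 116 per active arm (435/3 = 145, 80% evaluable) or 148 (174 under 2:2:1, 85% evaluable).
- Counts uniform on 5 to 20.
- Odds of clearance multiplied by 0.87 or 0.92 for each additional lesion.

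**Step 1: is the unadjusted comparison valid?** Trials were simulated with 35% clearance, count and location both prognostic, and only chance imbalance. The mean unadjusted difference was within about 0.002 of the truth. At a true difference of 0.20 with 145 per arm, it wrongly passed in 3.6% to 4.6% of trials. A second set at 30% clearance gave 3.2% to 3.7%. All are below the nominal 5%.

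**Step 2: how precise is the planned interval?** The half-width is 1.645 × √(2p(1−p)/n) + 1/n.

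| n per arm | SE | 1.645 × SE | 1/n | Half-width | Largest passing difference |
|---|---|---|---|---|---|
| 116 | √(0.42/116) = 0.0602 | 0.0990 | 0.0086 | 0.108 | 0.092 |
| 148 | √(0.42/148) = 0.0533 | 0.0876 | 0.0068 | 0.094 | 0.106 |

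**Step 3: how far could PP selection on count move the difference?** Suppose one active arm keeps 90% of subjects with 5 to 12 lesions but only 70% of those with 13 to 20, while the other keeps 90% throughout. In the first arm the low-count share rises from 0.5 to 0.9/(0.9 + 0.7) = 0.5625. The shift is 0.0625 × (clearance in the low half − clearance in the high half).

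- Odds ratio 0.87: 0.0625 × (41.1% − 18.9%) = 1.38 points.
- Odds ratio 0.92: 0.0625 × (36.9% − 23.1%) = 0.86 points.

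If 80% are kept instead of 70%, the low-count share is 0.9/1.7 = 0.5294 and the shifts are 0.65 and 0.40 points. Counting smaller lesions as well raises the largest shift to 1.47 points. Against the SE of 6.02 points at 116 per arm, that is 1.47/6.02 = 0.24 of one standard error.

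**Step 4: what would adjustment do in an ordinary trial?** With chance imbalance only, adjusted and unadjusted estimates differ with an SD of 1.0 to 2.0 points. At true differences of 0 or 6 points they reach opposite conclusions on ±0.20 in 2% to 10% of trials. When count has no effect at all, they still disagree in 0.6% to 2.6%. The two ranges overlap, so a single disagreement may be noise at the boundary.

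**Step 5: what would adjustment miss?** If PP loss depends on something not recorded, the unadjusted and adjusted estimates were both off by 1.5 points in the simulated example. Agreement between them would not show that PP selection was harmless.

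**The case for a change.** The best case for the extra analysis is pre-specification. A baseline table can show an imbalance but not how far it moved the treatment difference. If the PP arms do differ on count, a regulator may ask for an adjusted estimate, and a model chosen after unblinding carries less weight than one named beforehand. The data exist, the cost is a short SAP paragraph and some programming, and a standardised risk difference could be read directly against ±0.20. The disagreement rates in Step 4 are not zero. A separate set of assumptions, with stronger prognostic effects and a true difference of 0.10, gave 9.4% to 12.1%, although part of that came from leaving the continuity correction off the adjusted interval. In the example of Step 3, adjustment removes the shift completely.

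These points stand as reasons why a sponsor might choose to add the analysis. They do not make its absence a fault. The selection pattern in Step 3 requires one of two double-blind 2.5% imiquimod arms to lose 30% of its high-count subjects while the other loses 10%, and nothing in the documents points to that. The unadjusted result would still decide equivalence, so a disagreement would only be discussed. The version with a real gain, making the adjusted analysis primary, would raise equivalence power by 0.5 to 3.6 points if count is prognostic and lower it by 0.1 to 0.6 points if it is not. It would also depart from the criterion in Protocol 17.3.1. Location adds little, because no document gives clearance by site. Carrying the continuity correction over to a model-based interval would be an improvised step that neither document provides for.

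**Conclusion.** The concern does not hold. The unadjusted comparisons are valid, they match between protocol and SAP, and they keep false equivalence below 5% under every setting examined. Following the plan as written gives a sound conclusion. Where PP selection on lesion count is constructed to matter, it moves the difference by 0.4 to 1.5 points, at most about a quarter of one standard error. Count imbalance will be visible by arm in both populations, and the supportive ITT comparison gives a second view.

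These sizes rest on assumed clearance, arm sizes and prognostic effects. Stronger effects or heavier differential loss would enlarge them. The allocation sentences and SAP 8.5 and 8.9 have unreadable text, so a stratification factor or an adjusted analysis may already be there. The conclusion does not depend on that, because the comparisons are adequate without one.

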17. STATISTICAL CONSIDERATIONS

17.1 Sample Size

ioequivalence was concluded if the 90% continuity-corrected confidence interval on the difference in active treatment complete clearance rates was between -0.20 and +0.20 in the per protocol (PP) population, and each active treatment was found to be statistically superior to the vehicle by independent continuity-corrected Z-tests in the intent-to-treat (ITT) population.

total of 435 ITT subjects
for demonstrating superiority of each active treatment over the vehicle treatment.

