8.6 Screening and Baseline Assessments

8.6.1 Demographic and Baseline Characteristics

Gender, age (derived), race and ethnicity will be summarized by treatment group for the ITT and PP populations. The number in each of the following age groups will also be summarized by treatment group for the ITT and PP populations: 18-40, 41-64, 65-75, and >75. Age will be calculated as floor[(screening date - date ofbirth)/365.25].

The size of the Treatment Area (in centimeters) at Baseline will be determined from an estimate of the %BSA treated, the subject's height and weight using the Mosteller formula. Characteristics of the AK lesions in the Treatment Area at Baseline will be summarized including the total number of AK lesions and the number of AK lesions at least 4 mm in diameter.

Informed consent information and subject eligibility status will be provided in a listing.

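### Does the continuity correction on the primary tests and interval cost enough power to justify removing it?

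*SAP*

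**What the plan says.** The rule for superiority is in SAP 8.7.1: "Two-sided, continuity-corrected Z-tests will be used to evaluate the superiority of each active treatment's complete clearance rate", with success requiring each active arm to be above and "statistically different (p<0.05) from, the Vehicle proportion in the ITT population at EOS". For equivalence the same section says "The 90% Wald's confidence interval with Yate's continuity correction will be constructed on the difference (generic imiquimod minus Zyclara) in the proportions of subjects", to be read against -0.20 to +0.20 in the PP population. Protocol 17.3.1 carries the same two methods ("Two-sided, continuity-corrected Z-tests will be used to evaluate the superiority of each active treatment's clearance proportion"; "The 90% Wald's confidence interval with Yate's continuity correction will be constructed on the difference between the proportions of subjects with lesion clearance").

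Protocol 17.1 states the sample-size criteria in the same corrected terms: "90% continuity-corrected confidence interval on the difference in active treatment complete clearance rates was between -0.20 and +0.20" for equivalence, and each active arm "statistically superior to the vehicle by independent continuity-corrected Z-tests in the intent-to-treat (ITT) population" for superiority. It gives 435 ITT subjects in total. The allocation ratio, planning rates and power do not appear in the readable text, and gaps there are not a fault of the plan. Neither document says whether the Z-test uses a pooled or an unpooled variance.

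**The concern.** Therapeutic equivalence needs three things at once: both superiority tests at p<0.05 in ITT, and the interval inside the margin in PP. One missed superiority test sinks the claim. The correction shrinks each observed active-minus-vehicle difference and widens the equivalence interval, so the tests spend well under their 5%. An uncorrected pooled test already holds close to 5% at these sample sizes. It is natural to ask why the sponsor should give up power when a change of wording would recover it, and whether an unstated variance form leaves a primary p-value open to choice.

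**Working it through.** **Inputs.** From the documents: two-sided 0.05, a 90% interval, margin 0.20, and 435 ITT subjects in three arms. Assumed: 1:1:1 (145 vs 145) or 2:2:1 (174 vs 87), both of which divide 435 exactly; vehicle clearance 5%-15%; active 20%-40% (one extra row below uses 15%); 116 to 174 PP subjects per active arm (0.8 × 145 = 116; 0.8 × 174 ≈ 139).

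**The plan's own figure.** 435 cannot be reproduced or refuted, because its inputs are not readable. It is compatible with corrected sizing: the corrected two-proportion formula gives exactly 435 for 20% vs 5%, 90% power, 2:2:1 (5 × 87), where the uncorrected formula gives 385. It also gives 435 for 27% vs 10%, 95% power, 1:1:1 (3 × 145). At least 80 assumed scenarios fall within 3%, so this does not show which one was used.

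**Formulas.** Correction c = ½(1/n1 + 1/n2), which is 1/145 = 0.0069 for 145:145 and ½(1/174 + 1/87) = 0.0086 for 174:87.
- Superiority: Z = (|pA − pV| − c)/SE. Pooled SE = √[p(1−p)(1/n1 + 1/n2)]; unpooled SE = √[pA(1−pA)/n1 + pV(1−pV)/n2].
- Equivalence: difference ± (1.645 × unpooled SE + c).

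**A single data set.** Take 36/145 active and 22/145 vehicle. The difference is 14/145 = 0.0966, pooled p = 58/290 = 0.20, and SE = √(0.16 × 2/145) = 0.0470. Uncorrected Z = 0.0966/0.0470 = 2.06, p = 0.040. Corrected Z = (0.0966 − 0.0069)/0.0470 = 1.91, p = 0.056. The verdict can flip, but this example sits in the narrow band where it does.

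**Error rate of the superiority test** (exact enumeration of two binomials, common rate 5%-15%).

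| Test | Two-sided error rate |
|---|---|
| Corrected, pooled | 2.1%-3.3% |
| Corrected, unpooled | 2.4%-3.6% |
| Uncorrected, pooled | 4.5%-5.1% |
| Uncorrected, unpooled, 174:87 | up to 6.4% |

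**Power, 145:145, pooled, corrected to uncorrected.** 30% vs 15%: 0.841 to 0.874. 25% vs 10%: 0.907 to 0.931. 20% vs 5%: 0.970 to 0.982.

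**Power, 174:87.** The last two columns show what an uncorrected pooled test gains over each possible reading of the planned test.

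| Active vs vehicle | Corrected pooled | Corrected unpooled | Uncorrected pooled | Gain if planned test is pooled | Gain if unpooled |
|---|---|---|---|---|---|
| 30% vs 15% | 0.730 | 0.772 | 0.781 | 5.2 points | 0.9 |
| 25% vs 10% | 0.814 | 0.854 | 0.855 | 4.1 | 0.1 |
| 20% vs 10% | 0.478 | 0.548 | 0.547 | 7.0 | −0.05 |
| 20% vs 5% | 0.919 | 0.948 | 0.946 | 2.7 | −0.2 |
| 15% vs 5% | 0.619 | 0.730 | 0.703 | 8.4 | −2.7 |

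The largest pooled gains occur where power is poor under either test. At 30% vs 10% the pooled gain is only 0.4 (145:145) or 1.2 points (174:87).

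**Equivalence interval** (exact, clearance 20%-40%). Corrected coverage is 91.8%-92.6%, and false equivalence at a true 20-point difference is 3.4%-4.2%. The correction costs 1.6-4.2 points of power at 116 per arm, 0.6-2.3 at 139, 0.5-1.9 at 145 and 0.1-1.0 at 174. Without it, the Wald interval reaches 5.8% at the margin. A Miettinen-Nurminen interval runs at 4.6%-5.3%, above 5% in 23 of 36 settings. The degenerate case of 0% vs 20% is left out; there the planned interval itself reaches 5.6%.

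**Stratifying by baseline lesion count.** The count will be available ("Characteristics of the AK lesions in the Treatment Area at Baseline will be summarized including the total number of AK lesions"), but under an assumed lesion model a stratified Cochran-Mantel-Haenszel (CMH) test changed superiority power by only −0.5 to +0.7 points.

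**The case for a change.** The best case for acting is the unstated variance form. At 174:87 and 30% vs 15%, the corrected test has power 0.730 pooled and 0.772 unpooled, and the two give opposite verdicts in about 4.3% of trials (0.4% at 145:145). A primary p-value should not hang on an unwritten programming choice, and one clause would settle it.

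The fact stands, but it is missing detail, not a fault in the method. Under the assumed inputs, both forms stay at or below 3.6% once corrected, so neither reading inflates the error rate. A pooled variance is the usual companion of a Yates-corrected test, and fixing the form in the programming specification before unblinding is ordinary practice. A clause in SAP 8.7.1 would be tidy but optional.

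It can also be said that the conservatism does not depend on the assumptions. That is true: over common rates of 2%-50% the corrected pooled error rate runs from about 0.8% to 4.0%, always below 5%. Conservatism alone, though, does not show that power is short.

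**Conclusion.** No change follows. The correction is prespecified, consistent across both documents and part of the stated sample-size criteria, so its cost cannot be called a loss against plan. Under the assumed allocations and a 5%-15% vehicle rate, the superiority tests run at about 2.1%-3.6% and the interval covers about 92%.

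What removal would recover is uncertain: 2.5 to 3.4 points at 25% vs 10% and 30% vs 15% with 145 per arm (pooled). With 174:87 it is 4 to 5 points in those two cases if the planned test is pooled, and at most 1 point if unpooled, turning negative elsewhere. Against that stands weaker error control: uncorrected Wald up to 5.8%, uncorrected unpooled Z up to 6.4%, Miettinen-Nurminen up to 5.3%. Editing Protocol 17.3.1 would also need an amendment with IRB approval (Protocol 18.4). The SAP ties its equivalence concept to a draft guidance (section 4, footnote 1) that cannot be checked here, so the regulator would have to agree to a different interval. The added stratum brings no useful gain. An uncorrected pooled test could be reported as supportive if the sponsor wishes, but the primary analyses can stand as written.
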